- Use of any psychotropic medication
- History of a fish allergy
- History of a medical condition that decreases coagulability
- Use of anticoagulant medication

Design

Secondary/Archival Data Analysis Survey/Questionnaire Research Interviews and Focus Groups Prospective Clinical Research

Study Procedures

Recruitment/Participant Identification Process:

Healthy, adult females will be recruited from the surrounding community through posting of flyers and word of mouth. All rules for posting flyers will be followed at every institution we canvass. Potential subjects will initially be screened over the phone by the study coordinator within a week of potential subjects calling the study voicemail number listed on the flyers. The PI will review every phone screen to ensure that potential participants meet the most basic inclusion criteria for this study.

Informed Consent:

Description of location(s) where consent will be obtained:

Consent will be obtained in-person at the Brain Institute's clinical location at the University Neuropsychiatric Institute.

Description of the consent process(es), including the timing of consent:Once the subject is deemed eligible for the study, consent will be obtained from the subject before any study-specific procedures are complete. During the consent process, participants will be able to take as long as they need to ask questions, read and sign the consent form.

Procedures:

The study is designed for a one-month completion. Potential subjects will be screened in a 10-20 minute phone interview to determine eligibility. The first visit will involve subjects reviewing and signing the consent form prior to engaging in any study procedures. All procedures listed are for research purposes only.

Subjects will provide a urine sample for drug screening and a blood sample for serum glutamic oxaloacetic transaminase (SGOT) and serum glutamic pyruvic transaminase (SGPT). A visual acuity test will be given as well as weight and height measurements. The physical assessments will take approximately 30 minutes to complete. Neuropsychological and clinical rating scales will be administered as well, taking approximately 1 hour and 30 minutes. Each of the two visits should take approximately 2 hours to complete. The subjects will then be given their complete supply of citicoline, creatine and omega-3 tablets and instructed to take a combined daily dose over the next 28 days. They will be asked to return after 14 days for additional neuropsychological testing and clinical measures that will take approximately 1 hour. After 28 days, subjects will return for a repeat of measures for a second 2-hour evaluation session.

Each participant will be given a supplement log at the end of visit 1. They will be asked to complete the log during the 28 days to indicate that the daily dose of supplements were taken according to instructions. The study coordinator will check the log on the second and third visits as well as count the remaining supplement pills. If participants do not comply with the daily supplement schedule, then the PI will determine if the participant should be withdrawn from the study.

Clinical Assessment

The Mini International Neuropsychiatric Interview (M.I.N.I.) will be administered to each subject. The M.I.N.I. is a diagnostic interview designed to assess basic functioning and symptoms for lifetime psychiatric disorders. Subjects meeting diagnostic criteria for any psychiatric disorder, past or current Axis I or II, will not be included in the study. The Positive and Negative Affect Scale (PANAS) will be given to each subject as a self-evaluation scale in which subjects will rate their current feelings and emotions. Mood and life style questionnaires will also be given to each subject. The Columbia Suicide Severity Rating Scale (C-SSRS) will also be administered at each visit. Finally, the Monitoring of Side Effects Scale (MOSES) will be given to study participants during the second and third visit to assess for any treatment side effects. If a subject becomes upset or uncomfortable during any part of the clinical assessment, they will be offered a chance to

take a break as well as other resources/referrals to help. They will also be reminded about how their confidentiality and privacy are protected as well as the voluntary nature of the study. The clinical assessment portion of the study should take approximately 30 minutes.

Neuropsychological Testing

In addition to the clinical rating scales to be completed, the proposed investigation also includes a battery of neuropsychological tests designed primarily to evaluate general intellectual capacity, executive/attentional functions, and memory processing. A trained psychometrician will administer these measures. All test scoring will be completed blind to subjects' treatment group status and clinical ratings. The neuropsychological tests were chosen because they are standard, well-known measures that can be administered and scored reliably. Given the importance of accurately obtaining IQ estimates from subjects, we will administer four subtests from the WAIS III. These neurocognitive measures are well known to the principal investigator, and previous studies have demonstrated reliable performance (Maher, Manschreck, Woods, [name], & Tsuang, 1995; Pope & [name], 1996; [name] & Kinney, 1993). The measures include the following: Wechsler Adult Intelligence Scale (WAIS-IV): WAIS-IV Vocabulary Subtest, WAIS-IV Information Subtest, WAIS-IV Digit Span Subtests, WAIS-IV Block Design Subtest; WAIS-IV Coding Subtest; WAIS-IV Symbol Search Subtest; California Verbal Learning Test (CVLT)/ California Verbal Learning Test (CVLT-C); Rev-Osterreith Complex Figure Test (ROCFT); Continuous Performance Test (CPT); Stroop Color-Word Test; Trail Making Test; The Wisconsin Card Sort Test (WCST).

WAIS-IV Vocabulary Subtest: This subtest of the Wechsler Adult Intelligence Scale-Revised measures the subject's verbal ability and has been shown to be highly correlated with measures of general intellectual ability.

WAIS-IV Information Subtest: This subtest assesses the general knowledge of persons who grew up in the United States. The items are arranged in order of difficulty, from the simplest to the most difficult, which few adults could answer. It measures verbal skills, breadth of knowledge, and remote memory. It reflects formal education and a motivation for academic achievement. Among brain injured populations, information tends to be one of the least affected measures and can therefore serve as an estimate of premorbid ability.

WAIS-IV Digit Span Subtest: This subtest primarily measures the efficiency of attention. A subject repeats a string of digits presented by the experimenter. In the first part the subject repeats the digits forward; on the second part the subject repeats the numbers in reverse sequence. Failure on one of the two trials of this may be due to distraction, non-cooperation, inattentiveness or lack of concentration. Repetition backwards uses "working memory" and involves mental double-tracking in that both the recall of the number sequence and the reversing operations must proceed simultaneously.

WAIS-IV Block Design Subtest: This test of visuoconstructional ability is recognized as a test of visuospatial planning and function. It has been shown to be correlated with measures of general intellectual ability. In this test, the subject is presented with identical red and white blocks and asked to construct 8 designs presented to him on a stimulus card. The blocks are made up of distinguishable faces, 2 red sides, 2 white sides,

and 2 red & white sides split diagonally. Concrete minded persons have particular difficulty constructing the designs with diagonal patterns.

WAIS-IV Coding Subtest: This subtest assesses visual-motor coordination, motor and mental speed.

WAIS-IV Block Symbol Search Subtest: A series of paired groups, each pair consisting of a target group and a search group. The examinee indicates, by marking the appropriate box, whether either target symbol appears in the search group.

California Verbal Learning Test (CVLT): This verbal learning test assesses the subject's immediate and delayed recall, as well as suggesting the strategy utilized for retrieval of newly-learned information. Subjects are asked to remember a 16-item word list, which is presented on five trials. After each trial, the subject is asked to recall all of the words that they can remember. A second list is then presented to provide an interference condition. The subject is then asked to recall the first word list. After a temporal delay, the subject is again asked to recall the first word list. Test results provide scores for assessing verbal learning, strength of memory following interfering tasks, proactive interference, accuracy of recognition memory and storage versus retrieval of newly learned information.

Continuous Performance Test (CPT): This classic test of sustained attention has been adapted to a computerized version that can be administered to study subjects in 14 minutes. A subject is required to attend vigilantly to a series of visual stimuli and to indicate when target stimuli appear, disregarding distracter stimuli in which the target stimuli are embedded. This task generates measures of reaction time, omission errors, and commission errors, as well as an index of overall performance. Poor performance on the CPT has been associated with a number of psychiatric disorders. Scores include reaction time, omission errors, and commission errors, as well as an index of overall performance.

Rey-Osterreith Complex Figure Test: This complex figure test is an assessment of visuo-organizational ability, visual attention, and visual memory. The subject is asked to copy a complex figure, which is then evaluated for strategy, constructional accuracy, and detail reproduction. After removing the stimulus and the copy, the subject is asked to reproduce what he can recall from the figure. Approximately 30 minutes later, he is asked again to reproduce the figure. The complex design can be scored in both recall conditions on the basis of the number of elements, which have been correctly recalled. The difference between immediate and delayed performance scores is a measure of temporary decay for visuospatial memory.

Stroop Color-Word Test: This test measures the ability to inhibit inappropriate responses and resist interference. This test procedure includes three sections (color naming, word reading and interference) and is designed to establish competing response tendencies within the study subject and to assess the ability to suppress the interfering stimuli. Dependent measures include both reaction time to complete each condition, as well as total errors of omission and commission per condition. Difficulty with inhibition is reflected by an increase in errors and/or time in the interference section relative to the color naming or word reading sections.

Trail Making Test: This test is designed to measure visual conceptual and visuomotor tracking, as well as maintenance of cognitive set. The subject must first draw lines to

connect consecutively numbered circles on one work sheet (Part A) and then connect the same number of consecutively numbered and lettered circles on another work sheet by alternating between the two sequences (Part B). Trails B is the more sensitive of the two tests -- particularly to frontal-lobe dysfunction -- as scores on this section are indicative of the subject's ability to shift sets and process concurrent stimuli.

The Wisconsin Card Sort Test: The Wisconsin Card Sort Test (WCST): This test assess a person's ability to form abstract concepts, utilize feedback, and to shift and maintain set, and has been used extensively in the evaluation of patients with frontal lobe damage, as it has been shown to be sensitive to frontal dysfunction. The test consists of 4 stimulus cards, varying in color, geometric form, and number. Without a time limit, the subject has to match each of the cards in the deck to a key card. No explanation is given to the subject as to the criterion being used in making a match. For each attempt, the subject is told if the trial is a correct or incorrect match. After each sequence of ten correct responses, the tester changes the match criterion without giving warning to the subject. Total number of categories correct, perseverative and other error types are dependent variables.

Procedures performed for research purposes only:

Statistical Methods, Data Analysis and Interpretation

This study is designed to explore whether oral supplementation of citicoline, creatine, and omega-3 fatty acids in combination for one month will result in cognitive improvements that correlate with brain activation and metabolism changes in 20 healthy adult females, ages 40-60. Data will be expressed as mean \pm standard deviation, except where noted. Variables will be compared using ANOVAs with a=.05. All statistics will be computed using SPSS version 11.0 for the Macintosh. We will also examine the association between neuropsychological measures of attention, cognitive inhibition and memory as well as clinical measures for mood.

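### Tests that depend on new material or an undiscovered rule are repeated within 28 days, with no alternate forms and no handling of practice, so day-28 change mixes the intended function with carry-over from visit 1

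*Combined protocol and SAP*

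**What the plan says.** The Procedures text under Study Procedures sets three visits. Every subject receives the full supplement supply at visit 1. At the middle visit, "They will be asked to return after 14 days for additional neuropsychological testing and clinical measures that will take approximately 1 hour"; the tests for that hour are not listed. At the end, "After 28 days, subjects will return for a repeat of measures for a second 2-hour evaluation session".

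The Neuropsychological Testing section describes each instrument once, without reference to visit:

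- **WCST:** "No explanation is given to the subject as to the criterion being used in making a match", and "After each sequence of ten correct responses, the tester changes the match criterion without giving warning to the subject". Its outcomes are defined: "Total number of categories correct, perseverative and other error types are dependent variables".
- **CVLT:** "Subjects are asked to remember a 16-item word list, which is presented on five trials". A second list serves as interference, and the first list is then recalled again, both immediately and after a delay. The scores are said to bear on newly learned information.
- **Complex figure:** the figure is copied, and then "After removing the stimulus and the copy, the subject is asked to reproduce what he can recall from the figure". It is drawn from memory once more about 30 minutes later.

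The Statistical Methods section specifies ANOVAs at .05 in 20 women, looking for cognitive improvement. Alternate or parallel forms, counterbalancing, practice effects and reliable-change corrections appear nowhere. The list of measures names the CVLT together with the CVLT-C, but assigns neither to a visit. The testing section mentions scoring blind to treatment group, but no groups are defined and no untreated women are described.

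**The concern.** These three tests lose part of their meaning when the subject has met them before. A woman who learned at visit 1 that the sorting rule changes after a run of correct matches does not have to discover this again at day 28. A word list heard five times and recalled repeatedly, or a figure copied and drawn twice from memory, is not wholly new four weeks later if the same one is used.

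Executive function and memory are among the functions the battery is designed to evaluate, and the analysis looks for improvement. Carry-over is likely to move mean recall and card-sorting scores in that same direction. An inert supplement could then appear beneficial on scores that matter to the study, and nothing in the plan would show that the gain came from prior exposure.

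**Working it through.** **Step 1. What the text fixes and what it leaves open.**

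| Test | Why novelty matters, by the protocol's own description | Is reuse of content stated? |
|---|---|---|
| WCST | Rule unexplained, shifts unannounced | Not in words, but it follows closely: one procedure is described and the measures are repeated |
| CVLT | Scores newly learned information | No. One target list is described; the form at each visit is not given |
| Complex figure | Recall of a figure after it is removed | No. One figure is described; the form at each visit is not given |

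The CVLT and complex-figure part of the point is therefore that the form is unspecified. A site following the text has no instruction to change it.

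**Step 2. How large the effect could be.** The plan has no effect size, SD, retest correlation or power statement, so there is no figure of its own to reproduce. The following is an illustration.

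Inputs from the documents: n = 20 and alpha = .05.

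Assumptions: two-sided paired t-test (equivalent to an ANOVA with two time points), no supplement effect, a mean retest gain of d baseline SDs, and a retest correlation r between 0.6 and 0.8.

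Formulas: standardised paired change dz = d / √(2(1 − r)); noncentrality = dz × √20; critical value t(19) = 2.093; chance of significance from the noncentral t distribution.

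Worked case, d = 0.5 and r = 0.6: √(2 × 0.4) = 0.894; dz = 0.5 / 0.894 = 0.559; noncentrality = 0.559 × 4.472 = 2.50; chance = 0.66.

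| Assumed gain d | r = 0.6 | r = 0.7 | r = 0.8 |
|---|---|---|---|
| 0.1 SD | 0.08 | 0.09 | 0.10 |
| 0.2 SD | 0.16 | 0.20 | 0.27 |
| 0.3 SD | 0.30 | 0.38 | 0.52 |
| 0.5 SD | 0.66 | 0.78 | 0.92 |

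With no retest gain, each entry would be the nominal 0.05. The rates are per score.

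**Step 3. What the table measures.** It shows how often an uncontrolled before-after test would call a mean retest gain significant. It does not measure how far day-28 scores depart from the intended function; the documents contain no data on that.

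**Step 4. What counterbalancing does.** Suppose two forms differ by δ in mean score, 10 women take A then B, and 10 take B then A. Expected change is T + δ in one half and T − δ in the other, where T is the change over time. The average is T, so the form difference cancels from the mean. It still adds about δ² to the variance of individual change, since half the women are shifted up by δ and half down. A form term in the ANOVA removes that at the cost of one degree of freedom (19 to 18).

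**The case against.** The strongest reply is that much of this is inference. Repeating the measures means giving the same tests, and that is compatible with a different list or figure each time. This stands for the CVLT and the figure: a reader might infer that identical material is reused, but the documents do not say so. It has little force for the WCST, where changing the cards would not conceal a rule already discovered.

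Three further stronger readings are tempting and also lack support:

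- A reader might infer that day-28 scores measure memory of visit 1 instead of the intended function. The text supports only a mixture, in unknown proportion.
- A reader might infer that every woman is pushed towards improvement on every score. A positive mean gain does not imply that. Some scores have no clear direction: complex-figure decay is the difference between two recalls, both of which prior exposure could raise, and proactive interference on the CVLT need not improve when the first list is better known.
- A reader might infer that the three tests are given a third time at day 14. The tests for that visit are not listed.

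It can also be said that the percentages reflect the missing comparator, since a control group with the same mean gain would cancel it. That is right about the percentages. A control group would not make the material new again, however, so the content of the day-28 scores is worth protecting in its own right. Finally, in an exploratory study, dropping WCST change altogether would be a debatable trade-off; the fix below does not require it.

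**Conclusion.** The concern holds in a limited form. Three novelty-dependent tests, the WCST most clearly, are repeated within 28 days in women who all receive the supplement. No forms are specified and practice is not addressed. Change at day 28 on these tests mixes the intended function with carry-over, and mean recall and card-sorting scores are likely to move towards apparent benefit.

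The size is unknown. Under the stated assumptions, gains of 0.3 to 0.5 SD would give a false signal in about 30% to 92% of studies per score, against a nominal 5%; a gain of only 0.1 SD would give about 8-10%. Both the gains and the correlations are assumed. The protocol should be changed on this point, because the remedy is cheap and the affected scores belong to named targets of the battery.

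**What to change.** 1. Specify a different CVLT list and a comparable alternate complex figure at each re-test. Counterbalance form order across the 20 women (10 in each order if day 28 is the only re-test), and include form as a term in the ANOVA.
2. List the tests for the day-14 hour. If it would include the CVLT, the complex figure or the WCST, leave those three out, so that day 28 is the only re-exposure.
3. The WCST may stay at both main visits, but report its change as descriptive and not as evidence of supplement benefit.
4. State in the analysis section that alternate forms reduce carry-over of content but not familiarity with the procedure. Without a concurrent control, any remaining improvement on these or the other repeated tests cannot be attributed to the supplement.

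The cost is protocol wording and alternate test materials, with no extra visit or staff. The downsides are slight added noise where forms are not perfectly equivalent, one degree of freedom for the form term, and a weaker conclusion on the WCST.

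### Read literally, the plan's one ANOVA rule also covers the safety data, and comparing visit means in 20 women is insensitive to harm confined to a few of them

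*Combined protocol and SAP*

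**What the plan says.** The section on statistical methods, data analysis and interpretation is one short paragraph. On presentation it says "Data will be expressed as mean \pm standard deviation, except where noted". On comparison it says "Variables will be compared using ANOVAs with a=.05". The only other analysis is an association between neuropsychological and mood measures. The sample is 20 women.

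The safety data are described elsewhere. Under Procedures, visit 1 includes "a blood sample for serum glutamic oxaloacetic transaminase (SGOT) and serum glutamic pyruvic transaminase (SGPT"). For day 14 the text says "They will be asked to return after 14 days for additional neuropsychological testing and clinical measures"; no blood sample is named there. For day 28 it says "After 28 days, subjects will return for a repeat of measures for a second 2-hour evaluation session". Under Clinical Assessment, "the Monitoring of Side Effects Scale (MOSES) will be given to study participants during the second and third visit", and the C-SSRS is given at every visit.

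No section provides a count of affected women, a shift table, a reporting threshold or a per-woman listing for any of these measures. Every participant appears to receive the supplements ("The subjects will then be given their complete supply of citicoline, creatine and omega-3 tablets"), so the comparison available is between visits within one group.

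**The concern.** Liver-enzyme rises, side effects and suicidality tend to appear in a few individuals rather than as a shift in everyone. A test of means handles that pattern badly: the few large values raise the mean, but they also raise the standard deviation in the denominator, so the test statistic has a ceiling. If the one stated rule were followed for the safety data, a marked rise in two or three women would probably yield a non-significant result, and nothing else in the plan would bring those women into the report.

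**Working it through.** **Inputs.** From the documents: n = 20, alpha = .05, the ANOVA F test (non-directional), one treated group. Inferred: two enzyme time points, day 0 and day 28. The plan states no SD, effect size or power, so there is no figure of its own to reproduce.

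**Ceiling on the statistic.** Let k women have the same rise x and the other 20 - k no change.

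- Mean change = kx/20
- Variance of change = (kx² - k²x²/20)/19 = x²·k(20 - k)/(20·19)
- Squared standard error = x²·k(20 - k)/(400·19)
- F = t² = (k²x²/400) / [x²·k(20 - k)/(400·19)] = 19k/(20 - k)

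The size of the rise, x, cancels. The critical value F(.95; 1, 19) is 4.381.

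| k of 20 | F = 19k/(20 - k) | t | p (1, 19 df) | p if visits treated as independent (1, 38 df) |
|---|---|---|---|---|
| 1 | 19/19 = 1.00 | 1.00 | .33 | .32 |
| 2 | 38/18 = 2.11 | 1.45 | .16 | .15 |
| 3 | 57/17 = 3.35 | 1.83 | .083 | .075 |
| 4 | 76/16 = 4.75 | 2.18 | .042 | .036 |

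Three equal rises (15% of the women) stay above .05; four do not.

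**Dependence on the unstated ANOVA type.** The limit is also 3 for every number of completers from 10 to 20, and for a 10 v 10 between-group comparison (k = 3: p = .065). It drops to 2 with a one-sided t test (k = 3: p = .041) or an uncorrected three-visit ANOVA (k = 3: p = .046). The plan specifies neither, and names no day-14 blood sample.

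**Finite rises with background variation.** The closed form is a limit. Simulation with an assumed SD of 6 units for background change gives these chances of p < .05:

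| Rise (units) | k = 1 | k = 2 | k = 3 | k = 4 |
|---|---|---|---|---|
| 20 | 4.6% | 8.6% | 16.7% | 32.3% |
| 50 | 1.0% | 4.2% | 15.8% | 50.4% |
| 100 | 0% | 0.1% | 6.2% | 66.5% |
| 500 | 0% | 0% | 0% | 99.3% |

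With an assumed SD of 5, k = 3 is detected in about 13% of trials at a rise of 50 and 3% at 100. So up to three affected women are usually missed, and for three the chance of detection falls as the rise grows.

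**Unequal rises.** Rises of 100, 100, 100 and 400 with 16 zeros: mean 700/20 = 35; variance (190,000 - 24,500)/19 = 8,710.5; standard error sqrt(8,710.5/20) = 20.87; t = 1.68, p = .110. Five rises of 50, 50, 100, 400 and 600 give p = .102. More than three can be missed.

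**MOSES.** It is given only at visits 2 and 3, so there is no baseline. An ANOVA across visits could compare only day 14 with day 28, and a side effect present to the same degree at both would show no difference.

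**What counts would show.** Exact (Clopper-Pearson) 95% limits: 0/20 gives 0 to 1 - .025^(1/20) = 16.8%; 1/20 gives 0.1% to 24.9%; 3/20 gives 3.2% to 37.9%.

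**The case against.** The strongest reply is about scope. The ANOVA sentence follows an aim about cognition and precedes a sentence on neuropsychological and mood measures, and it names no safety variable. One can fairly read it as covering only those outcomes. That stands: the safety data come under it by default, because it is unqualified and nothing else is offered. On the narrower reading they have no planned analysis at all, and the same fix is needed.

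Second, blood is named only at visit 1, next to screening-type assessments, and could be an eligibility check. This also stands. A repeat is implied: the physical assessments (30 minutes) and the testing and rating scales (90 minutes) add up to the 2 hours given for both the first and the day-28 sessions. It is not stated. With a baseline sample only, the enzyme calculation applies to nothing; the points on MOSES and C-SSRS remain.

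Third, a reader might infer that a rise of any size in three women can never reach .05. That holds only where background change is negligible beside the rise; moderate rises are occasionally detected, as the simulation shows.

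Fourth, a reader might infer that the trial will declare the combination safe on a non-significant test. The documents state no tolerability conclusion. Their remark on minimal side effects concerns previous investigations, and the stated aim is functional effects.

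Finally, staff might notice an abnormal value when it arrives. The documents describe no such review, and it would not change what the analysis reports.

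**Conclusion.** The point holds in conditional form. Applied as written, the only analysis rule puts data collected to detect side effects through a comparison of means that is insensitive to harm in a few women. For enzymes, up to three of 20 with equal, large rises would probably leave the result non-significant (p = .083 in the limit for three, .042 for four). This rests on a day-28 sample, a non-directional two-visit test, and rises large relative to background change. The calculation covers enzymes only; for MOSES and C-SSRS the case rests on the absence of any count or listing and, for MOSES, of a baseline. The documents do not support saying that the plan deliberately chose ANOVA for safety. The change is worth making because it is nearly free.

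**What to change.** In the statistical section:

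- Limit the ANOVA sentence to the cognitive and mood outcomes.
- State that SGOT and SGPT are repeated at day 28, if that is intended.
- Report each woman's enzyme values at both visits, and the number who move from within to above the laboratory's upper limit, with an exact 95% CI. Note that 0/20 is compatible with a true rate of up to about 17%.
- Report MOSES findings at visits 2 and 3, and any positive C-SSRS item, as numbers of women with a listing, and acknowledge that MOSES has no baseline. Confidence intervals for each item are optional.
- State that a non-significant mean change is not evidence of safety.

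The cost is a few extra lines of text and reporting. If the day-28 blood sample is already intended, no new data, visits or staff are needed.
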